3.7.1.9 Acceptable Window for Testing

Observations/examinations and other procedures are to be performed within an acceptable window for testing, as specified in Table 3.7.1.9-1, with consideration of the availability of each subject for site visits, etc.

 Table 3.7.1.9-1
 Acceptable Window for Examinations/Assessment Period

The starting point of the antidepressant treatment period (Phase A) is the day of assessment at the initiation of the antidepressant treatment period (Phase A).

| Examination Point | Reference Day | Acceptable Window (From the Reference Day) |
|--|--|--|
| At screening | Day of assessment at the initiation of the antidepressant treatment period (Phase A) | Day -28 to -1 |
| Day of assessment at the initiation of the antidepressant treatment period (Phase A) | Day 1 | _ |
| Week 1 of the antidepressant treatment period (Phase A) | Day 8 | ± 2 days |
| Week 2 of the antidepressant treatment period (Phase A) | Day 15 | ± 2 days |
| Week 3 of the antidepressant treatment period (Phase A) | Day 22 | ± 2 days |
| Week 4 of the antidepressant treatment period (Phase A) | Day 29 | ± 2 days |
| Week 6 of the antidepressant treatment period (Phase A) | Day 43 | ± 2 days |
| Week 8 of the antidepressant treatment period (Phase A) | Day 57 | ± 2 days |
| At discontinuation | _ | _ |

At discontinuation: Performed within a possible window at a feasible time point.

 Table 3.7.1.9-1
 Acceptable Window for Examinations/Assessment Period

The starting point of the double-blind period (Phase B) is the day of assessment at Week 8 of the antidepressant treatment period (Phase A).

| Examination Point | Reference Day | Acceptable Window (From the Reference Day) |
|---|---------------|--|
| Day of assessment at Week 8 of the antidepressant | Day 1 | _ |
| treatment period (Phase A) | | |
| Week 1 of the double-blind period (Phase B) | Day 8 | $\pm 1 \text{ day}$ |
| Week 2 of the double-blind period (Phase B) | Day 15 | ± 2 days |
| Week 3 of the double-blind period (Phase B) | Day 22 | ± 2 days |
| Week 4 of the double-blind period (Phase B) | Day 29 | ± 2 days |
| Week 5 of the double-blind period (Phase B) | Day 36 | ± 2 days |
| Week 6 of the double-blind period (Phase B) | Day 43 | ± 2 days |
| At discontinuation | _ | _ |

At discontinuation: Performed within a possible window at a feasible time point.

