3.10 Definition of Completed Subjects

The treatment period is defined as the time period during which subjects are evaluated for safety and efficacy irrespective of whether the subject actually receives all doses of the IMP. Subjects who are evaluated at the last scheduled visit during the treatment period will be defined as trial completers. For the purposes of this trial, subjects who are evaluated at Week 6 of the double-blind period (Phase B) or antidepressant-responder treatment-continuation period (Phase A+) will be defined as trial completers.

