8.3 Subgroup Analyses

For the change from baseline (Week 8 of the antidepressant treatment period [Phase A]) in MADRS total score, the same MMRM analysis as that of the primary endpoint will be performed for each of the following subgroups.

For CYP2D6 phenotype, all subjects in the placebo group will be included in each subgroup.

- Requisite concomitant medication (duloxetine, escitalopram, fluvoxamine, milnacipran, paroxetine, sertraline, venlafaxine)
- Sex (male, female)
- Age (< 55 , ≥ 55)
- Number of adequate antidepressant drug treatments (1, 2, 3)
- DSM-5 diagnosis (single episode, recurrent episode)
- Frequency of major depressive episodes (1, 2, ≥ 3)
- Duration (in months) of the current episode (\leq median, $>$ median)
- Baseline MADRS total score (\leq median, $>$ median)

- Concomitant use of ultrashort-acting sedative-hypnotic drugs in the double-blind period (Phase B) (yes or no)
- Body weight (\leq median, $>$ median)
- BMI (\leq median, $>$ median)
- CYP2D6 phenotype (IM, EM)
- Impact of COVID-19 pandemic (subjects from whom consent was obtained before 07 Apr 2020, those from whom consent was obtained on or after 07 Apr 2020)

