9.2.2 Subgroup Analysis of Adverse Events

Numbers and proportions of subjects with TEAEs will be summarized by SOC and PT by treatment group and for the overall brexpiprazole group in each of the following subgroups:

- Requisite concomitant medication (duloxetine, escitalopram, fluvoxamine, milnacipran, paroxetine, sertraline, venlafaxine)
- Sex (male, female)
- Age (< 55, ≥ 55)
- CYP2D6 phenotype (IM, EM, PM, Unknown)

- Impact of COVID-19 pandemic (subjects from whom consent was obtained before 07 Apr 2020, those from whom consent was obtained on or after 07 Apr 2020)

9.2.3 Adverse Events in the Antidepressant Treatment Period (Phase A) and the Antidepressant-responder Treatment-continuation Period (Phase A+)

Numbers and proportions of subjects who experienced AEs in the antidepressant treatment period (Phase A) will be summarized by SOC and PT overall and for each requisite concomitant medication in the ADT set.

Numbers and proportions of subjects who experienced AEs in the antidepressant-responder treatment-continuation period (Phase A+) will be summarized by SOC and PT overall and for each requisite concomitant medication in the Phase A+ set.

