The mean plasma brexpiprazole concentration over time and individual values at each time point after the most recent dosing will be plotted by treatment group. Plotted diagrams by CYP2D6 phenotype in each treatment group and by requisite concomitant medication in each treatment group will also be provided in the same manner.

Scatter plots of plasma brexpiprazole concentrations over time will be provided by treatment group. Scatter plots by CYP2D6 phenotype in each treatment group and by requisite concomitant medication in each treatment group will also be provided in the same manner.

Plasma brexpiprazole concentrations below the lower limit of quantitation will be handled as 0 (ng/mL) when their descriptive statistics are calculated and when plotted diagrams and scatter plots are created.

11 Pharmacodynamic Analyses

Not applicable.

12 Pharmacogenomic Analyses

CYP2D6 genotype (phenotype) will be tabulated as specified in [Section 7.2 Demographic and Baseline Characteristics](#). CYP2D6 phenotype will also be summarized in subgroup efficacy and safety analyses.

13 Interim Analysis

No interim analyses are planned.

14 Changes in the Planned Analyses

- The following changes were made to categorical analyses of QTc:
Only subjects with postdose QTc meeting the criteria will be summarized, instead of summarization at all time points.

Only subjects with QTc not meeting the criteria at baseline and meeting the criteria after baseline will be summarized.
- It has been decided that CYP2D6 phenotype will be tabulated as specified in [Section 7.2 Demographic and Baseline Characteristics](#). CYP2D6 phenotype will also be summarized in subgroup efficacy and safety analyses.
- The original plan of using the LOCF dataset in ANCOVA of safety endpoints was changed as follows: Measurements at each time point and at the last assessment time point and, as necessary, the worst postdose measurement will be included in the analysis.
- The original plan of calculating descriptive statistics of plasma brexpiprazole concentrations by treatment group in pharmacokinetic analysis was changed as follows: Descriptive statistics of plasma brexpiprazole concentrations at each time point after the most recent dosing, trough concentrations, and plasma drug concentrations at all time points will be calculated by treatment group, by CYP2D6 phenotype in each treatment group, and by requisite concomitant medication in each treatment group.

15 References

Not applicable.

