CT-6.7.1 Summary of Mean Change From Baseline (End of Phase A) to Phase B by Study Week in MADRS Total Score by Duration of Current Episode: \leq Median - MMRM (Full Analysis Set)

CT-6.7.2 Summary of Mean Change From Baseline (End of Phase A) to Phase B by Study Week in MADRS Total Score by Duration of Current Episode: $>$ Median - MMRM (Full Analysis Set)

CT-6.8.1 Summary of Mean Change From Baseline (End of Phase A) to Phase B by Study Week in MADRS Total Score by Baseline MADRS Total Score: \leq Median - MMRM (Full Analysis Set)

CT-6.8.2 Summary of Mean Change From Baseline (End of Phase A) to Phase B by Study Week in MADRS Total Score by Baseline MADRS Total Score: $>$ Median - MMRM (Full Analysis Set)

CT-6.9.1 Summary of Mean Change From Baseline (End of Phase A) to Phase B by Study Week in MADRS Total Score by Ultrashort-acting Sedative-hypnotic Drugs: Present - MMRM (Full Analysis Set)

CT-6.9.2 Summary of Mean Change From Baseline (End of Phase A) to Phase B by Study Week in MADRS Total Score by Ultrashort-acting Sedative-hypnotic Drugs: Absent - MMRM (Full Analysis Set)

CT-6.10.1 Summary of Mean Change From Baseline (End of Phase A) to Phase B by Study Week in MADRS Total Score by Baseline Weight: \leq Median - MMRM (Full Analysis Set)

CT-6.10.2 Summary of Mean Change From Baseline (End of Phase A) to Phase B by Study Week in MADRS Total Score by Baseline Weight: $>$ Median - MMRM (Full Analysis Set)

CT-6.11.1 Summary of Mean Change From Baseline (End of Phase A) to Phase B by Study Week in MADRS Total Score by Baseline BMI: \leq Median - MMRM (Full Analysis Set)

CT-6.11.2 Summary of Mean Change From Baseline (End of Phase A) to Phase B by Study Week in MADRS Total Score by Baseline BMI: $>$ Median - MMRM (Full Analysis Set)

CT-6.12.1 Summary of Mean Change From Baseline (End of Phase A) to Phase B by Study Week in MADRS Total Score by CYP2D6 Metabolism Status: IM - MMRM (Full Analysis Set)

CT-6.12.2	Summary of Mean Change From Baseline (End of Phase A) to Phase B by Study Week in MADRS Total Score by CYP2D6 Metabolism Status: EM - MMRM (Full Analysis Set)
CT-6.13.1	Summary of Mean Change From Baseline (End of Phase A) to Phase B by Study Week in MADRS Total Score by Impact of COVID-19 Pandemic: Subjects Completed/Discontinued before 07APR2020 - MMRM (Full Analysis Set)

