CT-6.13.2	Summary of Mean Change From Baseline (End of Phase A) to Phase B by Study Week in MADRS Total Score by Impact of COVID-19 Pandemic: Subjects Completed/Discontinued on or after 07APR2020 - MMRM (Full Analysis Set)
CF-1	Mean Change From Baseline (End of Phase A) to Phase B by Study Week in MADRS Total Score - MMRM (Full Analysis Set)
CT-7.1.1	Extent of Exposure to Study Medication During Phase B (Safety Analysis Set)
CT-7.1.2	Extent of Exposure to ADT During Phase B (Safety Analysis Set)
CT-7.1.3	Extent of Exposure to ADT During Phase A (ADT Sample)
CT-7.1.4	Extent of Exposure to ADT During Phase A Plus (Phase A Plus Sample)
CT-7.1.5	Average Daily Dose ADT During Phase B (Safety Analysis Set)
CT-7.2	Summary of Treatment Compliance (Full Analysis Set)
CT-8.1	Adverse Events During Phase B (All Causalities) (Safety Analysis Set)
CT-8.2.1	Incidence of TEAEs During Phase B by MedDRA System Organ Class and Preferred Term (Safety Analysis Set)
CT-8.2.2	Incidence of Drug-related TEAEs During Phase B by MedDRA System Organ Class and Preferred Term (Safety Analysis Set)
CT-8.3.1	Incidence of TEAEs During Phase B by MedDRA System Organ Class, Preferred Term and Severity (Safety Analysis Set)
CT-8.3.2	Incidence of Drug-related TEAEs During Phase B by MedDRA System Organ Class, Preferred Term and Severity (Safety Analysis Set)
CT-8.4.1	Incidence of Deaths due to TEAEs During Phase B by MedDRA System Organ Class and Preferred Term (Safety Analysis Set)
CT-8.4.2	Incidence of Deaths due to Drug-related TEAEs During Phase B by MedDRA System Organ Class and Preferred Term (Safety Analysis Set)
CT-8.5.1	Incidence of Serious TEAEs During Phase B by MedDRA System Organ Class and Preferred Term (Safety Analysis Set)
CT-8.5.2	Incidence of Serious Drug-related TEAEs During Phase B by MedDRA System Organ Class and Preferred Term (Safety Analysis Set)
CT-8.6.1	Incidence of TEAEs Resulting in Discontinuation of IMP During Phase B by MedDRA System Organ Class and Preferred Term (Safety Analysis Set)
CT-8.6.2	Incidence of Drug-related TEAEs Resulting in Discontinuation of IMP During Phase B by MedDRA System Organ Class and Preferred Term (Safety Analysis Set)
CT-8.7.1	Incidence of TEAEs During Phase B of at Least 2% in Any Brexpiprazole Group and Greater Than Placebo by MedDRA System Organ Class and Preferred Term (Safety Analysis Set)

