CT-8.10.5	Incidence of TEAEs During Phase B by MedDRA System Organ Class and Preferred Term, by Impact of COVID-19 Pandemic (Safety Analysis Set)
CT-8.11.1	Incidence of TEAEs During Phase A by MedDRA System Organ Class and Preferred Term (ADT Sample)
CT-8.11.2	Incidence of TEAEs During Phase A Plus by MedDRA System Organ Class and Preferred Term (Phase A Plus Sample)
CT-9.1.1	Listing of Deaths During Phase B
CT-9.1.2	Listing of Deaths During Phase A and Phase A Plus
CT-9.2.1	Listing of Serious Adverse Events During Phase B
CT-9.2.2	Listing of Serious Adverse Events During Phase A and Phase A Plus
CT-9.3.1	Listing of Discontinuation of IMP due to Adverse Events During Phase B
CT-9.3.2	Listing of Discontinuation of IMP due to Adverse Events During Phase A and Phase A Plus
CT-10.1.1	Mean Change From Baseline (End of Phase A) in Clinical Laboratory Test Results - Serum Chemistry (Safety Analysis Set)
CT-10.1.2	Mean Change From Baseline (End of Phase A) in Clinical Laboratory Test Results - Hematology (Safety Analysis Set)
CT-10.1.3	Mean Change From Baseline (End of Phase A) in Clinical Laboratory Test Results - Urinalysis (Safety Analysis Set)
CT-10.1.4	Mean Change From Baseline (End of Phase A) in Clinical Laboratory Test Results - Prolactin, by Gender (Safety Analysis Set)
CT-10.1.5	Mean Change From Baseline (End of Phase A) in Clinical Laboratory Test Results - Other Tests (Safety Analysis Set)
CT-10.2.1	Shift Tables of Clinical Laboratory Test Results - Serum Chemistry (Safety Analysis Set)
CT-10.2.2	Shift Tables of Clinical Laboratory Test Results - Hematology (Safety Analysis Set)
CT-10.2.3	Shift Tables of Clinical Laboratory Test Results - Urinalysis1 (Safety Analysis Set)
CT-10.2.4	Shift Tables of Clinical Laboratory Test Results - Urinalysis2 (Safety Analysis Set)

CT-10.2.5 Shift Tables of Clinical Laboratory Test Results - Prolactin, by Gender (Safety Analysis Set)

CT-10.2.6 Shift Tables of Clinical Laboratory Test Results - Other Tests (Safety Analysis Set)

CT-10.3.1 Incidence of Laboratory Test Values With Potential Clinical Relevance During Phase B (Safety Analysis Set)

CT-10.3.2 Listing of Laboratory Test Values With Potential Clinical Relevance During Phase B by Subject (Safety Analysis Set)

CT-10.4.1 Incidence of Potential Hy's Law Cases During Phase B (Safety Analysis Set)

CT-10.4.2 Listing of Potential Hy's Law Cases During Phase B (Safety Analysis Set)

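### The COVID-19 subgroups are split by consent date in the SAP text but by completion date in the MADRS table titles; separately, the hypnotic subgroup is defined by use after randomisation

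*SAP*

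**What the plan says.** **COVID-19 subgroups.** SAP 8.3 lists, for the MADRS MMRM, "Impact of COVID-19 pandemic (subjects from whom consent was obtained before 07 Apr 2020" against those who consented on or after that date. SAP 9.2.2 uses the same rule for adverse events: "subjects from whom consent was obtained before 07 Apr 2020, those from whom consent was obtained on or after 07 Apr 2020". In Appendix 5 the two MADRS tables carry another rule. CT-6.13.1 reads "Impact of COVID-19 Pandemic: Subjects Completed/Discontinued before 07APR2020" and CT-6.13.2 reads "Subjects Completed/Discontinued on or after 07APR2020". The adverse-event table CT-8.10.5 says only "by Impact of COVID-19 Pandemic (Safety Analysis Set" and gives no date.

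**When completion occurs.** Protocol 3.10 counts as completers "subjects who are evaluated at Week 6 of the double-blind period (Phase B" (or of Phase A+). Protocol 3.7.1.9 puts that visit on Day 43 of Phase B, and Phase A Week 8 on Day 57 of Phase A. Screening takes place 1 to 28 days before Phase A starts.

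**Hypnotic subgroup.** SAP 8.3 also splits subjects by whether they took an ultrashort-acting sedative-hypnotic during Phase B. Protocol 3.7.1.4 randomises at the Week 8 assessment, so this use comes after randomisation. Protocol 4.3 allows it only in subjects who used such a drug in Phase A. CT-6.9.1 and CT-6.9.2 say present or absent and name no period.

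**The concern.** For COVID-19, one analysis has two definitions in current text. Which subjects enter two reported MADRS tables depends on whether the programmer follows the SAP body or the table titles. If the adverse-event table follows 9.2.2 and the MADRS tables follow their titles, tables with the same pandemic label would describe different subjects. A discontinuation date also falls after randomisation and can depend on treatment; a consent date cannot.

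For hypnotics, continuing or restarting in Phase B may respond to the assigned treatment or to sleep, and reduced sleep is a scored MADRS item (Protocol 3.7.2.1). The within-subgroup contrast is then not purely between randomised groups.

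**Working it through.** The plan gives no figure for either point. The 720 subjects, the difference of -2.4 and the SD of 7.7 used below come from its sample-size section, which reproduces: 2 x 7.7² x (1.960 + 1.282)² / 2.4² is just over 216, so 217 per group by the normal formula and 218 by the t-based one, against 218 stated.

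**1. Lag from consent to Phase B Week 6** (consent assumed on the screening day)

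- Screening: 1 to 28 days
- Phase A: Day 57 - Day 1 = 56 days
- Phase B: Day 43 - Day 1 = 42 days
- Nominal total: 1 + 56 + 42 = 99 to 28 + 56 + 42 = 126 days. The ±2-day window at each of the two visits widens this to 95 to 130.

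A completer with a 99-day lag is classified differently if consent fell from 30 Dec 2019 to 6 Apr 2020; with a 126-day lag, from 3 Dec 2019. Completion or discontinuation cannot precede consent, so every change runs from 'before' to 'on or after'.

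**2. How many subjects** (illustrative; uniform accrual from the planned start of 01 Jun 2018 is assumed)

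Subjects moved = 720 x lag / accrual length.

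| Accrual (assumed) | 99-day lag | 126-day lag |
|---|---|---|
| 913 days (30 months) | 78 | 99 |
| 1096 days (36 months) | 65 | 83 |
| 1395 days (46 months) | 51 | 65 |
| 1521 days (whole planned trial, 50 months) | 47 | 60 |

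With a 95-day lag the last row falls to 720 x 95/1521 = 45. The overall range is therefore roughly 45 to 100. As a share of the consent-date 'before' group: 01 Jun 2018 to 07 Apr 2020 is 676 days, so 99/676 = 14.6% to 126/676 = 18.6%. Phase B dropouts have a lag up to 42 days shorter, which changes the count by at most 720 x 0.07 x 42/913 = 2.3 subjects.

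**3. Hypnotic subgroup**

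Under Protocol 4.3 only Phase A users can be 'yes', and anyone still taking the drug when Phase B starts is 'yes' in every arm. Treatment can therefore change membership mainly among intermittent or stopped users.

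A simulation with a true effect of -2.4 and SD 7.7 shows what drives the bias in the 'yes' subgroup. The continuation rates, slopes and correlations are all assumptions.

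- Use unrelated to outcome: about -2.4, no bias.
- Use tied only to an early score (correlation 0.3 or 0.5 with Week 6; 70% or 90% 'yes'): about -2.3 to -2.4.
- The same, plus an assumed direct drug effect on hypnotic use of ±0.7 on the logit scale: -1.9 to -2.7.
- Deliberately strong model tying use to the Week 6 outcome itself, 70% 'yes': -2.0 to -2.3 with no direct drug effect, and -1.1 to -2.8 with ±0.7 added.
- Split by Phase A use instead: about -2.4 throughout.

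For scale, if 40% of 240 per arm used hypnotics in Phase A and 70% of them continued (both assumed), n = 67 per arm, and the 95% CI half-width is 1.96 x 7.7 x √(2/67) = 2.6 points.

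**The case against.** The best defence on COVID-19 is that this is a titling slip. Both body sections agree, the outlier is a list of table names, and other titles there are loose too: CT-6.6 refers to previous episodes where SAP 8.3 refers to frequency of episodes. The tables are subgroup outputs outside the tested sequence. The counts rest on an accrual pattern the documents do not give, and uniform accrual through a pandemic is doubtful. Completion date may even have been intended, since consent date puts subjects treated partly after 07 Apr 2020 in the 'before' group.

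Much of this stands: the importance is modest, the counts are illustrative and the choice of basis is partly judgement. It does not remove the contradiction. Nothing in the documents says that the body overrides the appendix, and two different dates give different subjects.

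A reader might infer that SAP 14, "Changes in the Planned Analyses", should have recorded the switch and that its silence is a further fault. The documents do not support that. Section 14 lists departures from the original plan, and the protocol of 23 Jan 2020 has no COVID-19 subgroup to depart from.

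On hypnotics, Protocol 4.3 already confines the issue to Phase A users, and no passage is contradicted. Both points are correct, which is why this part is only an improvement.

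**Conclusion.** The COVID-19 definitions are wrong as written: SAP 8.3 and 9.2.2 use consent date, CT-6.13.1 and CT-6.13.2 use completion or discontinuation date, and CT-8.10.5 is silent. That the two rules give different groups, with movement in one direction only, follows from the visit schedule. The figure of roughly 45 to 100 of 720 does not; it rests on assumed uniform accrual over 30 to 50 months.

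The hypnotic subgroup is a cheap improvement. A reader might infer that its estimate is seriously biased, but the documents give no data on hypnotic use, so size and direction are unknown. The bias is probably small: material bias appears in simulation mainly when the drug is assumed to change hypnotic use directly, and the subgroup interval is wide in any case.

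Neither part affects the primary test, alpha or sample size.

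**What to change.** Before unblinding:

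1. Reconcile the COVID-19 passages on one basis. Consent date is the natural choice: it matches both body sections and cannot be affected by treatment. Title and program CT-6.13.1, CT-6.13.2 and CT-8.10.5 accordingly, and footnote that this is not a clean split by pandemic exposure, because some 'before' subjects reach Week 6 on or after 07 Apr 2020.
2. In SAP 8.3, define the hypnotic subgroup before randomisation, either by use in Phase A or by use ongoing at the Phase B baseline. Both can be derived from the start and end dates recorded under Protocol 3.7.4. State the choice in the titles of CT-6.9.1 and CT-6.9.2. Each has a drawback: Phase A use counts subjects who stopped before Week 8, and baseline use misses those who restart.

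Cost: one line in SAP 8.3, five table titles, one footnote, the hypnotic derivation, and the COVID-19 derivation if it was programmed from the titles. No new data and no protocol amendment are needed.

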8.4 Exploratory or Other Analyses

The Cochran Mantel Haenszel (CMH) Row Mean Scores test of CGI-I scores will be performed on the LOCF dataset to compare each brexpiprazole group and the placebo group. The mean in each treatment group and the mean difference between each brexpiprazole group and the placebo group with their two-sided 95% CIs will be determined. The same analysis will be performed on the OC dataset.

The MADRS total score, CGI-I, CGI-S, mean SDS score and the score of each item, and MADRS-S total score at each time point in the double-blind period (Phase B) will be analyzed in the FAS in the same manner as for the primary and secondary endpoints. Descriptive statistics or frequency distribution of actual measurements and changes from baseline at each time point will be calculated by treatment group.

For MADRS total score, HAM-D 17-item total score, CGI-S, mean SDS score and the score of each item, and MADRS-S total score in the antidepressant treatment period (Phase A), descriptive statistics of actual measurements and changes from baseline (before the start of the antidepressant treatment period [Phase A]) will be calculated overall and for each requisite concomitant medication in the ADT set.

For MADRS total score, HAM-D 17-item total score, CGI-S, mean SDS score and the score of each item, and MADRS-S total score in the antidepressant treatment period (Phase A) and the antidepressant-responder treatment-continuation period (Phase A+), descriptive statistics of actual measurements and changes from baseline (before the start of the antidepressant treatment period [Phase A]) will be calculated overall and for each requisite concomitant medication in the Phase A+ set.

9 Safety Analyses

Safety analysis for the double-blind period (Phase B) will be performed using the safety analysis set. Unless otherwise stated, the safety analysis described in this section relates only to the double-blind period (phase B).

